# H00014860 Acetazolamide on High-Altitude Pulmonary Edema

Version 2 – 02/10/2018

## INVESTIGATOR STUDY PLAN

Secondary outcome measures: 2.) Time to completion of ultrasound exams

### 11. PROCEDURES INVOLVED\*

After informed consent has been obtained, subjects will be randomized to receive either of the study medications medication: 250mg of acetazolamide or a placebo pill. Investigator will be blinded as to which arm of the study the patient is enrolled. Medications will be obtained from the UMass Pharmacy in individual blister packs. We will ensure that acetazolamide and the chosen placebo pill look similar. Any identifying information on the blister pack will be obscured by a black marking pen, if necessary. Medications will then be inserted into small opaque envelopes and marked with only a number. Numbers will be assigned to medications by use of the random number generator function (=RANDBETWEEN(1,30\*)) (\*The final number will depend on the total number of subjects) in Excel with the top half of the list being assigned Acetazolamide and the bottom half placebo pill. The list will then be sorted in numerical order in Excel. When a subject enrolls, a number will be assigned in order. Blinding of the numbers and assigned medications as well as the assembly of the envelopes will be done prior to leaving UMass by PI's faculty advisor who will not be involved in medication administration.

At each of the time points noted in #9, lung ultrasound exams will be done at bedside in a private location to measure the total ultrasound lung comets (an ultrasound finding for pulmonary edema) for a "comet score." One (1) single dose of 250mg acetazolamide or placebo will be given at Everest Base Camp (Data Collection #4) and a comet score will be measured again 12 hours after acetazolamide or placebo is given. Previous studies have shown that comet scores increase with altitude and given that Everest Base Camp is the highest altitude the subjects will be residing at, it is believed that we will find the biggest decrease in comet score if acetazolamide is given at this point. The subject's heart rate and oxygen saturation will also be collected via a pulse oximeter.

Acetazolamide is a drug that has been approved by FDA for use of prevention of acute mountain sickness. Acetazolamide is not approved for prevention of HAPE and is investigational for this study. While it is FDA-approved to be used to treat acute mountain sickness, many previous studies and current guidelines have recommended the use of acetazolamide prevention HAPE. The investigation does not involve a route or dosage level that significantly increases the risks associated with the use of the drug product. This investigation does not involve a patient population that would significantly increase the risks associated with the use of the study drug.

Bedside ultrasound is a non-invasive modality of imaging that is routinely used and employed in clinical practice. It does not involve input of radiation into the subjects or an invasion of the subject's privacy. Subjects thoraces will be scanned in a private setting in lodging. Both left and right thoraces will be scanned. 28 total ultrasound images will be recorded during each session (16 on the right and 12 on the left). Please see attached WMS grant proposal page 2-5 for details of the methods of ultrasound scanning. Each session is expected to take approximately 5 minutes.

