**9. STUDY TIMELINES\***

**H00014860 Acetazolamide on High-Altitude Pulmonary Edema**  
**Version 2 – 02/10/2018**  
**INVESTIGATOR STUDY PLAN**

We will recruit subjects from the 2018 Wilderness Medical Society (WMS) Everest Base Camp Trek. The WMS 2018 Everest Base Camp Trek is a trekking trip from Lukla, Nepal (2840m) to Everest Base Camp (5400m) in Spring 2018. The duration of the trek is approximately 3 weeks. The duration of enrollment will be approximately 1-2 days during preparation part of the trip in Kathmandu, Nepal at the beginning of the trek. The estimated date for completion of primary analyses will be December 2018.

WMS Everest Base Camp Trek Itinerary

March 25	Arrival in Kathmandu, transfer to hotel (1310m)
March 26	Sightseeing in Kathmandu and preparation day **Enrollment day**
March 27	Fly to Lukla (2840m), trek to Phakding (2610m)
March 28	Trek to Namche (3440m) **Data Collection 1**
March 29	Namche and slow walk to Kunde Hospital/Kumjung
March 30	Extra day in Namche and visit Namche Bazar (3440m)
March 31	Trek to Tengboche (3860m)
April 1	Trek to Pheriche (4270m) **Data Collection 2**
April 2	Pheriche / hike Nakarsang Hill (5200m)
April 3	Pheriche
April 4	Lobuche (4910m) **Data Collection 3**
April 5	Gorakshep (5140m)
April 6	Hike to Kalapathar (5550m) / Everest Base Camp (5364m)
April 7	Everest Base Camp (5364m) **Data Collection 4 & 5**
April 8	Pheriche
April 9	Khumjung (3760m)
April 10	Manjo (2835m)
April 11	Lukla(2840m)
April 12	Fly back to Kathmandu
April 13	Kathmandu farewell dinner **Data Collection 6**
April 14	Final departure to home

\* May change slightly depending on weather, conditions, etc.

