#### **15. WITHDRAWAL OF SUBJECTS WITHOUT THEIR CONSENT\***

Subjects may be withdrawn from the study if they become exceedingly ill or injured, unconscious, or require evacuation. In this case, the data already collected will remain in the study, but subjects will not complete future data points.

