**25. LOCAL NUMBER OF SUBJECTS**

See #24. All subjects will be recruited from the Wilderness Medical Society 2018 Everest Experience Trek to Basecamp participants with a goal of 20-30 participants depending on the size of the CME trip registrants (exact number not available until registration closes in early 2018.)

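### Arms are assigned in Kathmandu about 12 days before the only dose, from one list-length block, so losses on the ascent become avoidable post-randomisation exclusions and can unbalance the arms

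*Combined protocol and SAP*

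**What the plan says.** All references are to the combined protocol and SAP.

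- **Time of assignment.** Section 11: "After informed consent has been obtained, subjects will be randomized", and "When a subject enrolls, a number will be assigned in order". Section 9: "The duration of enrollment will be approximately 1-2 days during preparation part of the trip in Kathmandu", with March 26 marked as enrolment day.
- **Time of dose.** Section 11 gives one dose, at Data Collection 4, and repeats the scan 12 hours later. The Section 9 itinerary marks April 7 at Base Camp as "Data Collection 4 & 5", and notes that dates may shift slightly.
- **Form of the list.** Section 11 describes one list, top half acetazolamide and bottom half placebo, sorted on an Excel random number. The example length is 30, to be adapted to the number of subjects. No blocks or strata are mentioned. The faculty advisor makes the code and packs the envelopes before the team leaves UMass.
- **Numbers.** Section 25 recruits "with a goal of 20-30 participants depending on the size of the CME trip registrants". That count is known once registration closes in early 2018. Consent is signed later, in Kathmandu (Section 30).
- **Losses.** Section 15: "Subjects may be withdrawn from the study if they become exceedingly ill or injured, unconscious, or require evacuation". Data already collected are kept and later time points are not. Section 16 also lets subjects withdraw at any time.
- **Analysis.** Section 13 names no analysis set, dropout allowance or replacement rule, and no rule for subjects randomised but not dosed.

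**The concern.** The primary outcome in Section 10 compares scans before and after the study medication. A subject who leaves the trek before Data Collection 4 has neither scan of that pair. That subject nevertheless has an arm, and so must be reported as randomised and then left out of the primary comparison, with no rule in the plan for doing so. Had the arm been assigned at Data Collection 4, the randomised set, the dosed set and the set with a pre-dose scan would be essentially the same people.

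The second consequence is balance. A half-and-half list gives equal arms only if every number is used and every subject is dosed. The plan secures neither, since the envelopes are packed before consent and illness on the ascent is foreseen. In a trial of 20 to 30 subjects, a few missing numbers can shift the split.

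A smaller matter is concealment. The faculty advisor who makes the code also travels on the trek (Section 23). While arms are already fixed, someone who made the code is on site during the weeks when illness and evacuation are being decided.

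**Working it through.** **1. The gap.** March 26 to March 31 is 5 days and March 31 to April 7 is 7, so 5 + 7 = 12 days. With the repeat scan 12 hours after the dose, a randomised subject can be lost over about 12.5 days. Assignment at Data Collection 4 would cut this to 12 hours.

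**2. The plan's own figure.** Section 13 states that 14 subjects give 80% power. It gives no effect size, standard deviation, sidedness or design, so the 14 cannot be reproduced. As an assumption, I read it as 7 per arm, two-sided alpha 0.05, two-sample t-test. Solving for 80% power with the noncentral t gives a standardised effect of d = 1.63. Section 13 names only a paired t-test for continuous variables, so this anchor is mine.

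**3. Imbalance.** I take each number as appearing once on the list and losses as unrelated to arm. For a list of length L, half per arm, with u numbers unused or lost, the number lost from one arm is hypergeometric. The difference between the dosed arms equals the difference among the u missing, so it cannot exceed u. The plan gives no loss rate; the losses below are assumptions.

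*List matched to 20 enrolled (10:10):*
- Up to 3 losses: a difference of 4 or more is impossible, 0%.
- 4 losses: all four must come from one arm. 2·C(10,4)/C(20,4) = 420/4845 = 8.7%.
- 5 losses: the total is odd, so the difference must be 5. 2·C(10,5)/C(20,5) = 504/15504 = 3.3%.
- 6 losses: split 5:1 or 6:0. 2·[C(10,5)·10 + C(10,6)]/C(20,6) = 5460/38760 = 14.1%.

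*List of 30 (15:15), 20 dosed, so 10 numbers missing:*
- Split 7:3 or more extreme. 2·Σ C(15,k)·C(15,10−k) for k = 0 to 3, over C(30,10) = 7363356/30045015 = 24.5%.
- If only 14 are dosed from that list, the same calculation gives 27.2%.

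**4. Power, at d = 1.63.** Average power is taken over the hypergeometric split.

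| Case | Equal arms | Average over chance splits | Loss (points) |
|---|---|---|---|
| List 20, 16 dosed | 85.8% | 85.4% | 0.5 |
| List 20, 14 dosed | 80.0% | 79.1% | 0.9 |
| List 30, 20 dosed | 93.2% | 92.7% | 0.4 |
| List 30, 14 dosed | 80.0% | 78.3% | 1.7 |

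(Losses are computed before rounding.) Individual splits of 14: 9:5 gives 76.6% and 10:4 gives 71.7%. A split of 10:4 or worse has probability 1.1% from a list of 20 and 6.6% from a list of 30.

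**5. Which change does what.** Late assignment from the same list uses the first m numbers of a random order. That has the same hypergeometric distribution, so 20 dosed from a list of 30 still gives 24.5%. Blocks with early assignment still lose balance when subjects drop out. With both, the arms at dosing differ by at most half a block: 1 for blocks of 2, 2 for blocks of 4.

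**The case against.** The strongest reply is that late assignment recovers nobody. A subject who leaves before Data Collection 4 lacks the scan pair under either scheme; what changes is who is counted as randomised. That stands: the gain is a clean randomised set and balanced arms, not more data.

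A reader might infer that these exclusions bias the comparison. The documents do not support that. No study drug is given before April 7, so it cannot cause the losses. Envelopes are opaque and carry only a number, and the investigator is blinded. Section 14 says participation will not alter treatment or evacuation. Section 11 keeps the faculty advisor out of giving the medication. What remains is that the person who made the code is on the trek, so concealment from everyone on site is not assured. That is a weakness, not evidence of bias.

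A reader might also infer that arm sizes are left wholly to chance. They are not. The list is in effect one full-length block, and the arms are exactly equal if all numbers are used and all subjects dosed. Section 11 also sizes the list to the number of subjects, so a 30-number list with 20 dosed is an unfavourable case. Registration can guide that sizing, but the numbers who consent and reach Base Camp cannot be known when the envelopes are packed.

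Finally, a reader might expect a real loss of power. On average it is small, as the table shows.

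**Conclusion.** The point holds as a low-severity design improvement. Assigning at enrolment creates avoidable exclusions between randomisation and dose, and the single list-length block does not protect balance once numbers go unused or subjects are lost. The chance of a difference of 4 or more runs from 0% when losses are few to about a quarter when a 30-number list yields 20 dosed subjects. Expected power falls by roughly 0.4 to 1.7 points in the cases examined; only an uncommon split such as 10:4 costs much, about 72% against 80%.

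These figures rest on assumed loss counts, on losses unrelated to arm, and on reading the 14 subjects as 7 per arm. The 12-day gap rests on the printed itinerary. No bias is shown. The case for change is that nothing in the documents calls for early assignment, and the alternative is nearly free.

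**What to change.** Make two changes to Section 11 together.

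1. At consent, give only a study ID. Assign the next numbered envelope at Data Collection 4, to subjects then present, after the pre-dose scan is stored.
2. Build the list in permuted blocks, with the block size withheld from field staff.

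Either change alone is incomplete: late assignment from the present list leaves the imbalance as it is, and blocking with early assignment leaves the exclusions and lets losses undo the balance.

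The cost is protocol wording and a re-sorted list. The envelopes have to reach Base Camp in any case, and the dose, its timing and clinical care are untouched.

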#### **23. RESOURCES AVAILABLE**

Principal Investigator: Design and oversee the project. Obtain funding and necessary approvals. Set up hand-held ultrasound tablets. Travel to Nepal and collect data. Acquire images. Publish results. PI is a residency-trained physician in emergency medicine, currently in completing emergency ultrasound fellowship with extensive experience in bedside ultrasonography. PI also has experience in backpacking and camping in remote environments as well as experience in international travel.

Faculty Advisor: Will accompany PI during the trek and oversee another research project. The faculty advisor has experience with conducting research in rural Nepal at the proposed site for multiple prior studies. The faculty advisor is fellowship-trained in wilderness medicine and has significant experience in backpacking and camping in remote environments, international travel including Nepal and Asia, required travel medications/vaccinations, and mountain trekking safety. The faculty advisor has knowledge of the culture, customs, and society in Nepal as well as some basic knowledge of the Nepali language. The faculty advisor also has significant experience ascending to high altitude, identifying and treating high altitude illnesses, and potential evacuation options should an emergency arise.

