#### **24. LOCAL RECRUITMENT METHODS**

Subjects will be recruited from the Wilderness Medical Society 2018 Everest Experience Trek to Basecamp participants. This is an annual CME trip organized by the Wilderness Medical Society in which participants ascend from Kathmandu to Everest Base Camp and return. The CME trip

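### Conditional black-out of blister packs, with pills required only to look similar, could reveal the arm at dosing to the person who acquires the outcome images

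*Combined protocol and SAP*

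**What the plan says.** All of the masking procedure is in section 11 (Procedures Involved).

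- **Who is blinded:** "Investigator will be blinded as to which arm of the study the patient is enrolled". Subjects and the later image reader are not mentioned.
- **Pills:** "We will ensure that acetazolamide and the chosen placebo pill look similar".
- **Packs:** "Any identifying information on the blister pack will be obscured by a black marking pen, if necessary".
- **Envelopes:** "Medications will then be inserted into small opaque envelopes and marked with only a number".
- **Preparation:** numbering and assembly are "done prior to leaving UMass by PI's faculty advisor who will not be involved in medication administration".

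The single dose is given at Everest Base Camp at Data Collection 4, and the comet score is measured again 12 hours later. Section 23 (Resources Available) lists among the principal investigator's tasks "Travel to Nepal and collect data. Acquire images". Section 21 places definitive image review after the trek, and section 26 assigns final interpretation to an expert reviewer. No section says who opens the envelope or hands over the dose.

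**The concern.** The numbered opaque envelope hides the arm only while it is closed. Once it is opened, the blind rests on the pack and the pill, and both standards are loose. A pen mark applied only where needed can itself become a label, and similar pills may still be told apart.

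The single dose is the only thing that separates the arms, so the change from Data Collection 4 to 5 is the one contrast that randomisation protects. The comet score comes from images acquired by hand by an investigator who may have seen the packs opened, in a study that expects its largest fall in score at this point. If the operator could tell the arms apart, the care taken in acquiring the second set of images could follow that expectation. A blinded reader could not undo this, because the reader sees only what was recorded.

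**Working it through.** The plan gives no figure on this point, so the check is whether its masking rules still protect the blind at each step.

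**Step 1: envelope closed.** The envelopes are opaque, carry only a number, and are prepared by someone who does not give the medication. Concealment is adequate here.

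**Step 2: envelope opened, pack visible.** The documents do not describe the printing on either product, so there are three possibilities:

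- *Neither pack carries identifying print.* No pen is used and the packs give nothing away on this account.
- *Both carry it.* Both are penned. Whether the marks look alike depends on where the print lies, because no common area is specified.
- *Only one product carries it.* Under the conditional rule only that product is penned, and the mark separates the arms. With 20-30 subjects split equally, that is 10-15 marked and 10-15 unmarked packs. Anyone who has seen one of each could sort all the rest.

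The rule as written permits all three. A rule that marked or repackaged every dose identically would exclude the third and settle the second.

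**Step 3: pill visible.** Section 11 requires similarity, not identity, and mentions neither over-encapsulation nor common repackaging. The remaining leak depends on how close the match is, which is not stated.

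**Step 4: who sees it.** The faculty advisor is excluded from administration, so someone else hands over the dose or the subject opens the envelope. The documents name nobody. Nothing assigns the task to the principal investigator, and nothing keeps the investigator from seeing pack or pill.

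**Step 5: how it could reach the outcome.** Each session records 28 images (16 right, 12 left), which limits the choice of views. Interpretation by an expert reviewer, with definitive review after the trek, limits bias in counting, although that reader's blinding is not stated. What remains is mainly acquisition.

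**Illustration only.** The documents give no size for such a bias. Suppose it shifted one arm by *b* standard deviations with no true effect. For a two-sided two-sample t-test at 0.05 with *n* per arm, the false-positive rate comes from the noncentral t distribution with 2*n* − 2 degrees of freedom and noncentrality *b*√(*n*/2). (Section 13 names a paired t-test; the two-sample form is used here because the question is a difference between arms.)

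- *b* = 0.25: *n* = 10, noncentrality 0.25 × √5 = 0.56, rate 8.3%; *n* = 15, noncentrality 0.25 × √7.5 = 0.68, rate 10.1%.
- *b* = 0.5: *n* = 10, noncentrality 1.12, rate 18.5%; *n* = 15, noncentrality 1.37, rate 26.2%.

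These values of *b* are assumptions. They show how a shift would act and do not estimate what would happen in this trial.

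**The case against.** The strongest reply is that the packing sentence covers any identifying print on either product, and that both medications come in blister packs from the same pharmacy. On that reading both arms would be treated alike, and the qualifier only saves needless work. This may well be what was meant. It stands to this extent: marking one arm only is possible under the text, but it is not planned.

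Three stronger readings are tempting, and the documents do not support them.

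- *That the principal investigator must be the one giving the dose.* Section 23 describes only the investigator and the advisor, which invites this inference. But section 14 gives the trip leaders a medical role and section 26 mentions an expert reviewer, so elimination does not identify the dosing person.
- *That subjects would recognise the drug.* Section 24 says "This is an annual CME trip organized by the Wilderness Medical Society", which suggests medically trained participants but does not say so. Each subject receives one pill with nothing beside it for comparison, and no route is evident from a subject's guess to a 12-hour comet count.
- *That the score itself would be read with knowledge of the arm.* The fixed image set, the expert reviewer and review after the trek all count against this. The scanning method is in a grant proposal that is attached to the plan but not available here, so the operator's freedom over each image cannot be judged.

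What remains after these replies is that the rule allows a difference between arms that one sentence could rule out, and that a leak at dosing cannot be repaired afterwards.

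**Conclusion.** The masking rule in section 11 is weaker than it needs to be and should be tightened before the doses are packed. It could reveal the arm when envelopes are opened, either because the packs are printed differently and only one kind is penned (an assumption) or because the tablets can be told apart. It would matter chiefly if the person acquiring the post-dose images sees them, which the plan neither states nor prevents. In the worst packaging case the allocation of all 20-30 subjects could be sorted; if packs and pills happen to match, nothing leaks. The resulting bias in the comet score cannot be sized. This is a risk left open by the wording. It does not show that the trial will be unblinded, and it should not be cited as such.

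**What to change.** In section 11, replace the conditional black-out sentence with one rule for both arms, for example: *Before departure, every dose, active and placebo, is removed from its original pack and placed in an identical, unprinted, opaque container; if the tablets can be told apart, both are over-encapsulated.* If repackaging is not feasible, the minimum is the same black-out over the same area of every pack in both arms, whether or not it carries print. That minimum deals with the pack but not with a visible difference between tablets.

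Add that, where existing trip personnel allow, the subject opens the envelope and takes the dose out of sight of the investigator who scans. This should not be made a condition that requires extra staff, since the advisor is already excluded from administration.

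The cost is a little pharmacy or advisor time for 20-30 single doses, at a stage when the advisor is already assembling envelopes, plus a short edit to section 11. The dose, its timing and the scanning schedule are unchanged.

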#### **13. Data Analysis and Management\***

Previous studies in lung ultrasonography suggest that a minimum of 14 subjects will be needed to provide 80% power to detect a statistically significant difference in ultrasound lung comets. Between 20-30 total subjects are expected.

For data analysis, Fisher's exact test will be used to compare categorical variables. Continuous variables will be analyzed with paired Student's t-test. Linear regression models will be used to assess correlations between ultrasound lung comets and vital signs. In all cases p values < 0.05 will be considered significant. Data will be reported as mean +/- SD

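### The envelope numbers are drawn with replacement, so as written about 12 of 30 (or 8 of 20) envelopes share a number with the opposite arm

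*Combined protocol and SAP*

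**What the plan says.** Section 11 (Procedures Involved) gives the only allocation procedure in the plan. In the order in which the steps would be carried out:

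- **Draw.** "Numbers will be assigned to medications by use of the random number generator function", the Excel formula being "RANDBETWEEN(1,30" with a note on the upper limit: "The final number will depend on the total number of subjects".
- **Arms.** The list is split "with the top half of the list being assigned Acetazolamide and the bottom half placebo pill".
- **Sort and assign.** "The list will then be sorted in numerical order in Excel. When a subject enrolls, a number will be assigned in order".
- **Label.** "Medications will then be inserted into small opaque envelopes and marked with only a number".

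The faculty advisor prepares the code and the envelopes before the team leaves UMass and takes no part in giving the medication.

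Section 13 (Data Analysis and Management) gives the size: "Between 20-30 total subjects are expected". It also says that "a minimum of 14 subjects will be needed to provide 80% power", without saying whether 14 is a total or a number per arm.

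**The concern.** The drawn integer is attached to the medication and is the only mark on the envelope. It therefore has to be unique if it is to identify a treatment. RANDBETWEEN does not deliver that, because each cell is drawn independently of the others. Sorting brings equal numbers together but does not separate them. Section 11 has no uniqueness check, redraw, tie-break, renumbering or second mark on the envelope.

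Two things follow if the text is carried out exactly. First, a number that falls on both an acetazolamide and a placebo envelope does not tell the analyst which treatment the subject received. Second, handing out numbers in order is undefined where a number is missing or occurs more than once.

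Knowledge of each subject's arm underlies any comparison of acetazolamide with placebo. The study is a single trek with one dose per subject and 20 to 30 subjects, so a subject whose arm is lost cannot be replaced.

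**Working it through.** The plan states no figure on this point, so there is none to reproduce.

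**Inputs**

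- N envelopes, N = 20 to 30 (section 13).
- Independent integers on 1 to N (section 11). Setting the upper limit equal to N is the natural reading of the note that it follows the number of subjects.
- N/2 envelopes per arm (section 11).
- Duplicates are not resolved. This is an assumption and applies to every figure on shared numbers below.

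**1. Chance that no number repeats:** N!/N^N.

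- N=30: 1.3e-12
- N=20: 2.3e-8

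**2. Distinct numbers:** N(1 − (1 − 1/N)^N).

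- N=30: 30(1 − (29/30)^30) = 19.15 used, so 10.85 never used
- N=20: 20(1 − (19/20)^20) = 12.83 used, so 7.17 never used

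**3. Envelopes that share a number with the opposite arm.** A given envelope avoids all N/2 envelopes of the other arm with probability (1 − 1/N)^(N/2), so the expected count is N(1 − (1 − 1/N)^(N/2)).

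- N=30: 30(1 − (29/30)^15) = 30(1 − 0.6014) = 11.96
- N=20: 20(1 − (19/20)^10) = 20(1 − 0.5987) = 8.03

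This is about 40% at either size. Sizes in between give 9.60 (N=24), 10.39 (N=26) and 11.17 (N=28).

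**4. Numbers that occur on both arms:** N(1 − (1 − 1/N)^(N/2))^2 = 4.8 (N=30) and 3.2 (N=20).

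**5. Spread between lists.** A simulation of 200,000 lists per size agrees with the expected values in step 3 and gives:

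| | N=30 | N=20 |
|---|---|---|
| Sharing with the opposite arm, 95% range | 5 to 19 | 2 to 14 |
| Traceable from the number alone, mean (95% range) | 18.0 (11 to 25) | 12.0 (6 to 18) |
| Chance that no number is on both arms | 0.0008 | 0.008 |
| Chance that fewer than 14 are traceable | 11% | 69% |

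The last row uses the plan's minimum of 14, read as a total. It is a secondary comparison.

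**6. Sensitivity to the upper limit.** If the limit stayed at 30 while only 20 envelopes were made, the expected count would be 20(1 − (29/30)^10) = 5.75 instead of 8.03.

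**7. The draws read as a sort key only.** Suppose the sorted rows were renumbered 1 to N. Every envelope would then be traceable, but ties would remain in the key. Acetazolamide rows start on top, so a sort that preserves the original order within ties puts acetazolamide first in each tie. Simulated under that assumed sort behaviour, the first envelope has about a 63% chance of acetazolamide and the last about 37%, at N=20 and at N=30, instead of 50%.

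**The case against.** The strongest reply is that the no-repair scenario is unlikely. One person prepares 20 to 30 envelopes by hand from a sorted list. With about 11 of 30 integers missing and about 5 on both arms, the problem would be hard to overlook. A repair would come before enrolment, by someone who does not give the medication, and redrawing without regard to arm would still be random. This stands as a comment on likelihood, and it is why the counts are conditional. It does not rescue the text: the repair would be improvised with number and arm both visible on the sheet, and nothing would record how it was done.

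A second reply is that the procedure resembles the usual spreadsheet shuffle, with the draw as sort key. That may have been the intent. But the text attaches the drawn numbers to the medications and mentions no renumbering. The sort-key reading also leaves an unspecified tie-break that can make allocation depend on enrolment order.

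A third is that sections 16 and 26 provide a unique subject identifier. It keeps subjects apart in the data, but nothing links it to the contents of an envelope.

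A fourth is that the minimum of 14 comes without an effect size, a standard deviation or a statement of total or per arm. That is fair, and the conclusion does not need the comparison.

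**Conclusion.** The concern holds. The allocation rule as written almost never yields unique envelope numbers. If duplicates are left in place and the upper limit equals N, the number fails to identify the arm for an average of 11.96 of 30 envelopes or 8.03 of 20, with wide variation from list to list. If they are repaired, arm identity can be preserved, but the allocation is no longer the documented one. The plan states a rule that gives the wrong result when followed, which is more than a missing detail. The text must be corrected before the envelopes are filled.

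**What to change.** Replace the numbering step in section 11 with a random permutation:

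1. List equal numbers of acetazolamide and placebo labels, N rows in all.
2. Give each row a random decimal key and sort the rows by it.
3. Paste the result as fixed values so that it cannot recalculate.
4. Number the sorted rows 1 to N, each number used once, and mark the envelopes accordingly.
5. Check that the numbers are unique, and keep a master list of number and arm.

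With unique numbers, no number is shared between arms at any N. Two optional additions are separate from this error: small permuted blocks, in case fewer subjects enrol than envelopes are prepared, and a sentence on where the code list is kept.

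The cost is minutes of work before departure and two or three sentences of protocol text. Drug supply, number of subjects, schedule and personnel do not change.
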